9. DATA ANALYSIS

9.1. Study Endpoints - Efficacy

Primary efficacy will be assessed on the basis of a binary outcome of overall preparation success or failure. For statistical analyses, the following definition of preparation success and failure will be used:

Definition of successful preparation:

1. Overall Cleansing Assessment by the colonoscopist (Section 4.6.2) of “Excellent” or “Good” and does not satisfy any of the following failure criteria.

Definition of failed preparation:

1. Overall Cleansing Assessment of “Fair” or “Poor” by the colonoscopist
2. Any subject who did not have a colonoscopy based on the Investigator’s assessment of the cleansing (subject report of insufficient fecal output, unclear fecal discharge, etc.) or due to preparation related adverse events.
3. Any subject for whom cleaning was not adequate for evaluation

Unevaluable Subjects:

Subjects who were dispensed a kit but withdrew from the study prior to taking any preparation (including subjects who were disqualified subsequent to Visit 1 based on screening laboratory results) are excluded from the efficacy and safety analyses. Any subject who completely or partially took study preparation but did not have a colonoscopy due to non-preparation related reasons (e.g. lack of insurance, inability to return for colonoscopy) will not be included in the efficacy analyses. All treated subjects will be included in the safety analysis.

Success rate will be analyzed using CMH Chi-square adjusting for the effect of investigator site. The formal hypothesis test result (p-value) for treatment difference will be presented together with a two-sided 95% confidence interval for the difference.

Null Hypothesis $H_0: P_1 - P_2 \leq D_0$ versus Alternative Hypothesis $H_1: P_1 - P_2 > D_0$,

where P_1 is the success probability in the BLI4700 group, P_2 is the success probability in the PREPOPIK group (reference or control group), and D_0 is the acceptable margin of equivalence, which we set equal to -10% .

If necessary, we will pool the smallest centers into a “small-centers” stratum until each treatment arm in the smallest stratum has at least ten subjects.

If the test for non-inferiority is statistically significant, we will conduct a test of the superiority hypothesis:

Null Hypothesis $H_0: P_1 - P_2 \leq 0$ versus Alternative Hypothesis $H_1: P_1 - P_2 > 0$.

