The two hypothesis tests are hierarchically structured so that the second test will be conducted only if the first test rejects the hypothesis of inferiority. Thus there is no need to correct the alpha levels of the tests for multiplicity.

Sensitivity analyses will be performed for the primary endpoint based on stratification groups outlined in Section 4.1.2.

Additional efficacy endpoints will include:

- Cleansing score by segment
- Number (%) of excellent preparations overall and by segment
- Adequacy of cleaning and need for re-preparation
- Duration of colonoscopy
- Volume of intraprocedural water needed to irrigate the colon
- Number (%) of procedures that reached the cecum
- Time to cecum

Secondary endpoints will be analyzed in a manner similar to the primary analysis using the CMH test adjusting for site effects for count (percentage) outcomes and two-way ANOVA with terms for treatment, site, and their interaction for continuous responses. No adjustment will be made for multiplicity in testing the secondary endpoints. P values will be presented for hypothesis tests, and two-sided 95% confidence intervals for estimates of treatment effects.

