9.3. Sample Size

Approximately four hundred (400) subjects will be randomly assigned via the minimization scheme to one of two preparations in a ratio of 1:1 (200 subjects per group) and undergo colonoscopy. Based on prior studies using a similar grading system, the success rate for PREPOPIK is expected to be no greater than 90%⁴. Assuming a similar success rate for BLI4700, a two-sided asymptotic 95% confidence interval for the difference in success rates between groups (BLI4700 – PREPOPIK) will result in a lower CI bound greater than -10%, with probability 90%. This result would establish the non-inferiority of BLI4700 to PREPOPIK for a non-inferiority margin of 10%.

Our sample-size calculations for equivalence tests with a binary outcome use the method of Chow et al⁵. If the PREPOPIK success rate is 90% and the BLI4700 success rate is also 90%, the sample size needed is n=310 (total across both study groups) for a non-inferiority margin of 10% and a target power of 90% with confidence 95%. Thus with n=400 subjects we will attain 80% power even with a dropout rate in excess of 20%.

In randomized studies, the purpose of the stratification is to eliminate the stratification factor from the error term, thereby potentially reducing variability⁶. Moreover, because the trial will use stratification in the design, for consistency we will employ a stratified test in the analysis. The CMH analysis on risk differences, by eliminating center effects, essentially renders the analysis equivalent to that of a single-center study. The sample-size calculation described above assumes a single stratum that is free of between-stratum variability and therefore effectively models the stratified analysis that we will conduct.

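### Section 9.1 names a CMH chi-square as the primary test, but it cannot test the -10% non-inferiority null; the valid confidence-interval rule appears only in the sample-size section

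*Combined protocol and SAP*

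**What the plan says.** Section 9.1 (Study Endpoints - Efficacy) names one analysis for the primary endpoint: "Success rate will be analyzed using CMH Chi-square adjusting for the effect of investigator site". It continues: "The formal hypothesis test result (p-value) for treatment difference will be presented together with a two-sided 95% confidence interval for the difference". The non-inferiority null is P1 - P2 <= D0, with P1 for BLI4700, P2 for PREPOPIK, and D0 a margin "which we set equal to -10" percent. The step to superiority (null P1 - P2 <= 0) reads: "If the test for non-inferiority is statistically significant, we will conduct a test of the superiority hypothesis". The section adds that "the second test will be conducted only if the first test rejects the hypothesis of inferiority".

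Section 9.3 (Sample Size) puts the criterion differently. It considers "a two-sided asymptotic 95% confidence interval for the difference in success rates between groups" which, if both rates are similar at 90%, "will result in a lower CI bound greater than -10%, with probability 90" percent, and says that this result would establish non-inferiority. It later describes the analysis as "The CMH analysis on risk differences, by eliminating center effects".

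Neither section gives a margin-shifted test statistic, a formula or variance for a site-stratified interval, or an explicit one-sided level for either hypothesis test.

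**The concern.** The CMH chi-square has as its null no treatment difference within any site. It contains no -10% term and, as a chi-square, has no direction. Section 9.1 names it in the sentence just before the formal p-value and states a shifted null just after, so a programmer working from 9.1 alone would compute a p-value that does not address that null. The interval, which could address it, is listed only as something to present.

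This is the confirmatory decision of the trial. If the rule is not fixed before unblinding, one dataset can be read in more than one way: by an equality p-value, by a shifted test at an unstated level, or by a CI whose stratification and variance are unstated.

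**Working it through.** **Inputs.** From Section 9.3: 200 subjects per arm, 90% success in both arms, margin 10%, two-sided 95% CI, 90% target power, stated total of 310. From Section 9.1: D0 = -10%. The documents do not give the number of sites. The main calculations are therefore unstratified; one simulation assumes 10 sites with 20 subjects per arm each.

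**1. The plan's own sample size.** With unpooled variance and a shifted null, n per arm = [p1(1-p1) + p2(1-p2)] × (z_alpha + z_beta)² / margin², where p1(1-p1) + p2(1-p2) = 0.09 + 0.09 = 0.18.
- One-sided 0.05, power 90%: 0.18 × (1.645 + 1.282)² / 0.01 gives 155 per arm, 310 in total. This matches the stated figure.
- One-sided 0.025 (the level of a two-sided 95% CI), power 90%: 0.18 × (1.960 + 1.282)² / 0.01 gives 190 per arm, 380 in total.

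So the trial was sized for the shifted null, not for equality. The one-sided level, however, differs between the 310 and the 95% CI.

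**2. Power of the CI rule at 200 per arm.** SE = sqrt(0.18/200) = 0.03. Power = Phi(0.10/0.03 - 1.96) = Phi(1.373) = 91.5%, in line with the stated 90%. Exact binomial enumeration also gives 91.5%. The 10-site simulation with a stratified risk-difference interval gives 91.2%.

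**3. The two criteria compared at 200 per arm** (exact enumeration, unstratified; the CI is the simple unpooled-variance interval)

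| True rates, BLI4700 vs PREPOPIK | Chi-square p < 0.05 (two-sided) | of which favours BLI4700 | Lower 95% limit > -10% |
|---|---|---|---|
| 90% vs 90% | 4.8% | 2.4% | 91.5% |
| 80% vs 90% (on the margin) | 81% | under 1 in a million | 2.7% |

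At 90% vs 90%, the CI shows non-inferiority while the chi-square is non-significant in 89% of trials. The 10-site simulation with a true CMH statistic agrees: 4.8% and 81% for the CMH test, 91.2% and 2.6% for the stratified interval.

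**4. Two example datasets** (unstratified)
- 176/200 vs 180/200: difference -0.02, SE = sqrt((0.88×0.12 + 0.90×0.10)/200) = 0.0313. The 95% CI is -8.1% to +4.1%. The shifted z is (-0.02 + 0.10)/0.0313 = 2.56, one-sided p = 0.005. The chi-square p is 0.52. The CI rule concludes non-inferiority; the named test is not significant.
- 172/200 vs 180/200: difference -0.04, SE = sqrt((0.86×0.14 + 0.90×0.10)/200) = 0.0324. The lower limit is -10.4%. The shifted one-sided p is 0.032 and the chi-square p is 0.22. Non-inferiority is met at one-sided 0.05 and fails at 0.025, so the level has to be stated.

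**The case against.** The best defence is that the plan, read as a whole, does not make an equality p-value the gate. Section 9.1 writes out the shifted null, gates on the test for non-inferiority, and requires the first test to reject inferiority, which a test of equality cannot do. Section 9.3 supplies the operational rule and speaks of a stratified test on risk differences. A sensible analyst would probably follow that. This stands, and it limits the point: a reader might infer that the plan has no valid non-inferiority criterion, or that its gate certainly tests the wrong hypothesis, and the documents support neither. What remains is that the analysis section names a test that cannot do the job, while the rule that can is in the sample-size rationale.

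Three other stronger readings also fail.
- The superiority test is not wrong in the same way. Its null boundary is zero, which is the CMH null. Two-sided p < 0.05 with the estimate favouring BLI4700 is a one-sided 0.025 test; only direction and level need stating.
- The 81% at 80% vs 90% is not a false non-inferiority rate. Essentially all of those results show BLI4700 significantly worse.
- Inflated error from a simple Wald interval is not established. Section 9.3 says asymptotic, which also covers score and Mantel-Haenszel intervals. Even for a Wald interval, the error on the margin with a 90% control rate is 2.7% against 2.5%. Larger excesses (3.0% and 3.4%) need control rates of 95% and 98%, above the ceiling of 90% that 9.3 expects for PREPOPIK.

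**Conclusion.** The point holds as an error of test specification in Section 9.1. The CMH chi-square named there cannot test P1 - P2 <= -10%, and 9.1 does not adopt the CI rule of 9.3 as its decision rule. The consequence at the planned size is that the named test and the intended criterion usually disagree when the preparations are equal: about 5% against about 91% success. Taken literally, the error would mainly deprive an equally effective BLI4700 of a non-inferiority conclusion; it would not admit an inferior product, unless a significantly worse result were misread as success.

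These figures assume 200 evaluable subjects per arm and the 90% success rates of Section 9.3. The stratified figures also assume 10 equal sites, which the documents do not state; they barely differ from the unstratified ones. The planned 400 subjects remain adequate: under the CI rule, power is 91.5%, and 84.6% if 20% are lost (160 per arm). The power claims in 9.3 therefore survive, although its 310 rests on one-sided 0.05.

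**What to change.** In Section 9.1:
- Replace the CMH chi-square as the non-inferiority test with the site-stratified Mantel-Haenszel risk difference (RD). Conclude non-inferiority if the lower limit of its two-sided 95% CI exceeds -10%, or equivalently if z = (RD + 0.10)/SE is significant at one-sided 0.025.
- Name a stratified variance estimator, such as Sato's, and use the same site strata (after the planned pooling of small centers) for test and interval.
- Test superiority by the same interval (lower limit above 0), or by the CMH test at two-sided 0.05 with the estimate favouring BLI4700.
- State that the ordinary CMH p-value is not the non-inferiority test.

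The cost is a few sentences, settled before unblinding, and standard software. No extra subjects are needed, and power at 400 stays about 91%. A stratified score interval is an acceptable alternative; it lowers power at 90% vs 90% by about 1.5 points, from 91.5% to 90.0%.

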3. STUDY PLAN

3.1. Study Design

This is a randomized, parallel, multi-center, single-blind study in adult subjects.

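### Continuous secondary endpoints: the ANOVA keeps the treatment-by-site interaction and does not say how the overall treatment effect is weighted across sites, which may needlessly widen the confidence intervals

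*Combined protocol and SAP*

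**What the plan says.** All the relevant text is in section 9.1 (Study Endpoints - Efficacy).

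- Continuous additional endpoints are analysed by "two-way ANOVA with terms for treatment, site, and their interaction for continuous responses". The listed endpoints of this kind are duration of colonoscopy, irrigation water volume and time to cecum.
- P-values are to be reported for the tests, with "two-sided 95% confidence intervals for estimates of treatment effects".
- Count or percentage endpoints use a CMH test adjusted for site.
- The link to the primary analysis is general: "Secondary endpoints will be analyzed in a manner similar to the primary analysis".
- For the primary CMH analysis there is a rule for small centers: if needed, "we will pool the smallest centers into a “small-centers” stratum until each treatment arm in the smallest stratum has at least ten subjects". Section 9.1 does not say whether the rule also governs the ANOVA.
- On multiplicity: "No adjustment will be made for multiplicity in testing the secondary endpoints".

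The section names no type of sums of squares, no LS-means, no site weights, and no rule for dropping the interaction. On sites, section 3.1 says only "This is a randomized, parallel, multi-center, single-blind study in adult subjects". The number and size of sites are not given anywhere.

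**The concern.** Once treatment, site and their interaction are all in the model, there is no single treatment effect until someone chooses how to average the site-specific differences. The common default, a Type III test or an LS-means difference, gives each of K strata the weight 1/K. A stratum of 20 subjects then counts as much as one of 150.

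Two things follow. First, the continuous and percentage endpoints would estimate different averages over sites, although section 9.1 describes the analyses as similar. Second, when the effect is common across sites, equal weighting is less precise than weighting by information unless all strata are the same size. What is at stake is the width of the intervals and the size of the p-values for three reported efficacy measures. In addition, a choice that affects the result is left to a software default or to a decision made after the data are seen.

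**Working it through.** **Inputs.** Total N = 400, allocated 1:1 (section 9.3). Pooling threshold of ten subjects per arm, hence 20 per stratum (section 9.1). Site numbers and sizes are assumptions. The documents state no SD, effect size, power or sample size for any continuous endpoint, so there is no plan figure to reproduce; the calculation in section 9.3 concerns the binary primary endpoint.

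**Formulas.** Let stratum k have m_k subjects per arm (n_k = 2m_k), with K strata and common residual variance σ².

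- Equal-weight effect: Var = (2σ²/K²) Σ(1/m_k).
- Additive model (treatment + site): Var = 2σ²/Σm_k.
- Variance ratio: R = (Σm_k)(Σ1/m_k)/K² = N Σ(1/n_k)/K².
- The interval widens by √R, apart from a negligible change in the t quantile. Effective N = 400/R.

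Under 1:1 allocation the CMH weight of a stratum, n₁n₀/(n₁+n₀), is proportional to its size. The additive model uses the same weights.

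**Check of the mechanism on simulated data.** Ten strata with 70, 30, 20, 15, 13, 12, 10, 10, 10, 10 per arm (sum 200):

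| Analysis | Estimate | SE | F for treatment |
|---|---|---|---|
| Interaction model, Type III | 0.4600 (equals the unweighted mean of site differences) | 0.121 | 14.4 |
| Interaction model, Type II | – | – | 21.6 |
| Treatment + site | 0.4682 (equals the size-weighted mean) | 0.100 | 21.8 |

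By formula, Σ1/m_k = 0.7245, so R = 200 × 0.7245/100 = 1.449 and √R = 1.204. The Type II row shows that the loss comes from equal weighting and not from the degrees of freedom spent on the interaction.

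**Fixed layouts.**

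- Equal strata (10 of 20 per arm, or 20 of 10 per arm): R = 1.00, no loss.
- One stratum of 110 and nine of 10 per arm: Σ1/m_k = 0.9091, R = 200 × 0.9091/100 = 1.818, √R = 1.348, effective N = 220.

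**Random site sizes.** 4,000 sets per setting, N = 400, gamma-multinomial sizes, smallest centers pooled until every stratum has at least 20 subjects. Mean R:

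| Sites | CV of size | R | √R | 400/R |
|---|---|---|---|---|
| 10 | 0.4 | 1.11 | 1.05 | 360 |
| 15 | 0.6 | 1.17 | 1.08 | 342 |
| 20 | 0.6 | 1.32 | 1.15 | 303 |
| 25 | 1.0 | 1.38 | 1.17 | 290 |
| 25 | 0.6 | 1.57 | 1.25 | 255 |
| 25 | 0.4 | 1.82 | 1.35 | 220 |

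For 10 to 15 sites and CV 0.4 to 1.0, R lies at about 1.1 to 1.3, so the interval is about 5% (√1.11 = 1.05) to 14% (√1.3 = 1.14) wider.

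**Why 25 sites is worst.** The average site has 400/25 = 16 subjects, below the 20 needed, so many sites are merged. At CV 0.4 the pooled stratum holds about 55% of subjects and receives about 13% of the weight. A hand check with 220 subjects in the pool and 180 spread evenly over seven other strata gives R = 400 × (1/220 + 7/25.71)/8² = 1.73, close to the simulated mean. With 25 sites R falls as sizes become more unequal (1.82, 1.57, 1.38 at CV 0.4, 0.6, 1.0), because fewer subjects then end up in the pool.

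**If pooling is not applied to the ANOVA.** For 8 to 30 sites with CV 0.5 to 1.0, the median interval ratio is 1.14 to 1.66, against 1.07 to 1.38 with pooling.

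**Power, for illustration only.** If a comparison had 80% power in the additive model, power under equal weighting would be Φ(2.80/√R − 1.96): 76% at R = 1.1, 69% at 1.3, 55% at 1.8.

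**The case against.** The strongest reply is that the plan lists model terms and does not prescribe equal weights. That stands. A reader might infer from the interaction term that equal weighting is already specified, but section 9.1 does not say so, and the same model tested with Type II sums of squares loses almost nothing (F = 21.6 against 21.8). Section 9.4.3 refers to a statistical analysis plan for other details, and the weighting could be settled in such a text; the documents reviewed contain none.

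A reader might also infer that the sites differ greatly in size and that small sites would drive the estimate. The documents support neither. Site sizes are not given, and in the worst case within the range examined it is the merged small centers that are under-weighted.

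Nor can a power loss be claimed against a planned target, since none exists for these endpoints. The 80% starting point above is an assumption.

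Two further points are fair. Under a common effect the equal-weight estimate is unbiased and only less precise. If effects truly differ by site, an equal-site average is a legitimate target. But then the plan should say that this is the target and why it differs from the size-weighted one used for the percentage endpoints.

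**Conclusion.** The point holds as an unspecified weighting combined with a model that invites an inefficient default. If the Type III or LS-means contrast is used and pooling is applied, the interval is about 5% to 14% wider for 10 to 15 sites and up to about 35% wider for 25 sites, over size CVs of 0.4 to 1.0; it is no wider at all when strata are equal.

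These figures assume N = 400, 1:1 allocation within each stratum, a common residual variance and a common treatment effect. Section 4.1.2 lists three stratification groups and does not name site, so balance within site is itself an assumption.

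The consequence is limited. Only additional endpoints without multiplicity control are involved. The non-inferiority and superiority tests of the primary endpoint use the CMH analysis and are untouched.

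**What to change.** In section 9.1, replace the interaction model as the source of the reported results: take the treatment estimate, p-value and 95% confidence interval from a model with treatment and site only. Fit the interaction in a separate model, solely to check consistency across sites. State whether the small-center pooling rule applies to the ANOVA.

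This brings the continuous endpoints into line with the size-weighted CMH analysis, and it is never less precise than equal weighting when the effect is common across sites. If the sponsor prefers to keep the interaction in the model, naming a Type II or size-weighted contrast would remove the same problem. The cost is one phrase on the model and one sentence on pooling, with no effect on data collection, subjects or the primary analysis, provided that it is settled before unblinding.

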9.2. Study Endpoints - Safety

Adverse Events:

All subjects who took preparation in any amount will be included in the safety analysis. All adverse events will be analyzed based on the principle of treatment emergence. A sign or symptom will be regarded as treatment-emergent if it was present prior to the first dose and subsequently worsened in severity, or was not present prior to the first dose but subsequently appeared.

In order to define treatment emergence for events with missing start or stop dates the following additional criteria will be used:

- if both the onset and resolution dates for a particular event are missing, then the event is considered treatment-emergent;
- if the onset date for an event is missing and the resolution date falls after the initiation of the first dose, then the event is considered treatment-emergent;
- if the onset date for an event falls after the initiation of the first dose and the resolution date is missing or present, then the event is considered treatment-emergent; and
- if the onset date for an event falls before the initiation of the first dose and the stop date is missing or present, then the event is not considered treatment-emergent.

Adverse events will be collected using MedDRA category designations for body system and preferred term. The number and percent of subjects who experienced each adverse event will be presented in a tabular form. Individual tables will be provided for treatment-emergent adverse events, treatment-emergent adverse events by relationship to study drug, and treatment-emergent adverse events by severity. The difference in adverse events between study populations will be tested by the Fisher's exact test together with a 95% confidence interval for the treatment effect estimate.

Vitals Signs and Physical Examination:

Vital signs and physical examination data will be summarized with descriptive statistics.

Laboratory Data:

Results of laboratory tests for the change from baseline (Screening) and treatment group differences will be tested using ANOVA. In addition, shift tables will be presented to describe changes in lab parameter values between screening and post-treatment time points using normal range categories (low, normal, high).

Symptom Scale Data:

Symptom Scale data for individual symptoms for Overall Experience (stomach cramping, stomach bloating, nausea and vomiting) will be presented categorically by severity and tested by Chi-Square test.

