4.4. Visits 4 and 5: Follow up of Adverse Events and Laboratory Results

Subjects with out of range laboratory values (that were not pre-existing at Visit 1) and/or ongoing adverse events at Visit 3 will return for follow up on Day 7 (+/- 2 days) and Day 30 (+/- 2 days). Subjects requiring follow-up for abnormal laboratory values must undergo repeat testing. Subjects returning due to ongoing adverse events should be assessed to determine if the event has resolved or is clinically stable.

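### Section 9.2: the fourth date rule has no exception for worsening, so it contradicts the plan's own definition of a treatment-emergent event

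*Combined protocol and SAP*

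**What the plan says.** Section 9.2 states the governing principle: "All adverse events will be analyzed based on the principle of treatment emergence". Its general definition has two limbs. One covers a sign or symptom that first appears after the first dose. The other covers one already there, "if it was present prior to the first dose and subsequently worsened in severity".

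Four date rules follow, introduced by: "In order to define treatment emergence for events with missing start or stop dates the following additional criteria will be used". In summary:

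- Rule 1: onset and resolution both missing, treatment-emergent.
- Rule 2: onset missing, resolution after the first dose, treatment-emergent.
- Rule 3: onset after the first dose, whatever the resolution date, treatment-emergent.
- Rule 4: "if the onset date for an event falls before the initiation of the first dose and the stop date is missing or present", not treatment-emergent.

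Rule 4 does not mention severity. Nothing says whether the definition or the date rules prevail when they disagree.

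On recording, Section 5.1 starts adverse event collection at consent and ends it 30 days after exposure. It lists onset, severity and duration among the items recorded for each event, and does not say how a later change in severity is captured. Section 4.1 places conditions ongoing at Visit 1 in the medical history.

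**The concern.** A pre-dose complaint that the preparation makes worse is what the worsening limb of the definition exists to catch. Rule 4 excludes it on its onset date alone. Two programmers could each follow Section 9.2 faithfully and classify the same record differently.

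At stake are the treatment-emergent tables (overall, by relationship and by severity) and any Fisher's exact comparison built on them. The comparison of safety is part of the study objective in Section 2, so the classification should be settled before unblinding rather than chosen afterwards.

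**Working it through.** The plan gives no figure to reproduce. The check sets the general definition beside the date rules for each combination of dates and severity. TE means treatment-emergent.

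| Onset | Stop date | Worsened after dosing | General definition | Date rules | Rule 4 with exception |
|---|---|---|---|---|---|
| Before dose | Missing | No | Not TE | Not TE | Not TE |
| Before dose | Missing | Yes | TE | Not TE (**conflict**) | TE |
| Before dose | After dose | No | Not TE | Not TE | Not TE |
| Before dose | After dose | Yes | TE | Not TE if rule 4 applies (**conflict**) | TE |
| After dose | Missing or present | n/a | TE | TE (rule 3) | TE |
| Missing | Missing | Unknown | Cannot decide on dates | TE (rule 1) | TE |
| Missing | After dose | Unknown | Cannot decide on dates | TE (rule 2) | TE |

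**Which conflict is certain.** The second row has a missing stop date, so it falls within the lead-in's own scope. The fourth row has both dates. The lead-in would leave it to the general definition, and it is in conflict only if the reference in rule 4 to a stop date being present is taken to override the lead-in. With the exception added, neither conflict remains.

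**Whether the certain case can occur.** Four things must hold together.

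1. The event is on record as an adverse event with onset before the first dose. Section 5.1 allows this, and Section 3.3 allows up to 30 days between screening and colonoscopy. Against it, Section 4.1 sends conditions ongoing at Visit 1 to medical history, and the schedule in Section 4.5 shows adverse event collection only from Visit 2.
2. It worsens after dosing.
3. The worsening stays on the original record. If it is entered as a new event, rule 3 counts it.
4. It closes with no stop date. This is possible: under Section 4.4 an ongoing event "should be assessed to determine if the event has resolved or is clinically stable", and collection then ends.

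The case is possible under the plan but needs all four.

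**Size.** The number of such subjects, k, is not derivable from the documents. If k affected subjects in an arm share the same event, its treatment-emergent incidence in that arm is understated by k/n. Section 9.3 plans n = 200 per arm undergoing colonoscopy. The safety population is everyone who took any preparation, so it may be larger, up to about 450/2 = 225 per arm from the summary sheet. One subject is therefore 1/200 = 0.50 or 1/225 = 0.44 percentage points. Purely as an assumption, k = 0 to 3 gives 0 to 1.5 points at n = 200 and 0 to 1.3 points at n = 225.

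**The case against.** The strongest reply is that the date rules are labelled as additional and apply to incomplete dates, so they can be read as filling gaps where the general definition cannot decide. That reading is reasonable, but the text does not state it. Rule 4 gives a definite answer in a case that the definition also decides, and the answers differ.

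The second reply is about reach, and it stands. The routes through medical history and new-event logging leave a narrow residue, mainly events that begin between Visit 1 and the first dose. Much of the safety information also has its own analysis. For laboratory values, "shift tables will be presented to describe changes in lab parameter values between screening and post-treatment time points". Symptom Scale data "will be presented categorically by severity and tested by Chi-Square test". Vital signs are summarised separately. The sentence "The number and percent of subjects who experienced each adverse event will be presented in a tabular form" may still bring an affected event into a general listing, although the governing principle points the other way.

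The third reply is that the exception alone is not enough, and this also stands. If the record holds one severity and one onset, an analyst may be unable to see that a worsening happened after dosing. The present definition needs the same information, so the recording gap exists already, but the fix has to address it.

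A reader might infer that rule 4 removes every worsened pre-dose event, including those with complete dates. The lead-in does not support that. A reader might also infer that serious event reporting or the stopping rule is weakened. Section 6 has its own reporting path and follows serious events to resolution. Section 8.3 works on preferred term and grade and does not mention treatment emergence.

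**Conclusion.** Section 9.2 is wrong as written, and the severity is minor. Rule 4 contradicts the general definition for an event with pre-dose onset and a missing stop date that worsens after dosing and stays on its original record. Extending this to events with complete dates depends on a reading that the lead-in does not favour.

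Few events are likely to be affected, and their number cannot be obtained from the documents. The percentages in the working show only what one to three subjects would amount to; they are not evidence that any will occur. It would be tempting to conclude that the safety comparison is biased towards one preparation. The documents do not support that, since the same rule applies in both arms and nothing shows that affected events would fall unevenly. Efficacy, sample size and alpha are unaffected.

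**What to change.** 1. In Section 9.2, end rule 4 with an exception: *unless the event worsened in severity after the first dose*.
2. In Section 5.1 or the eCRF instructions, require that the adverse event record show an increase in severity after dosing. One way is to enter the worsening as a new record with its own onset date. The original and new records should then be counted once, not twice.
3. Do not add a sentence giving the general definition precedence over all the date rules. Once the exception is in place it is unnecessary. It could also override rules 1 and 2, which deliberately count events with missing onset: an event with no onset date, but otherwise known to predate dosing and not to have worsened, would drop out.

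The cost is one clause and one recording instruction. Counts of treatment-emergent events may rise slightly. Nothing changes in the efficacy analysis or the number of subjects.
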